3.9.3.3. Electrocardiograms

Descriptive statistics for ECG parameters (heart rate, PR interval, RR interval, QRS interval, QT interval, and QTc interval) at baseline and change from baseline values at each scheduled assessment timepoint and at the end of the treatment period will be presented. QTc interval will be calculated using Fridericia ($QTcF = QT/(RR)^{1/3}$) corrections; if RR is not available, it will be replaced with 60/HR in the correction formula.

Electrocardiogram parameter values are considered PCS if they meet or exceed the higher-limit PCS criteria listed in Table 9. The number and percentage of subjects with PCS postbaseline ECG values will be tabulated. The percentages will be calculated based on the number of subjects with non-PCS baseline values and at least one postbaseline assessment. The numerator is the number of subjects with non-PCS baseline values and at least one postbaseline PCS value. A supportive listing of subjects with PCS values will be provided.

Table 9: Criteria for Potentially Clinically Significant (PCS) QTcF

Parameter	Criteria
QTcF	>450 to ≤ 480 msec
	>480 to ≤ 500 msec
	>500 msec
	Change from baseline >30 to ≤ 60 msec
	Change from baseline >60 msec

3.9.4. Abnormal Movement Scales

Extra pyramidal symptoms (EPS) will be evaluated as AEs and also as assessed by abnormal movement scales. Abnormal movement scales will include the following: Abnormal Involuntary Movement Scale (AIMS), Barnes Akathisia Rating Scale (BARS), and Simpson-Angus Scale (SAS).

Change from baseline in all abnormal movement scales, total scores and subscale scores will be summarized by visit.

Number and percentage of subjects meeting the criteria for treatment emergent Parkinsonism (SAS total score >3), for treatment emergent akathisia (BARS global clinical assessment of akathisia score ≥ 2), for treatment emergent dyskinesia (AIMS score ≥ 3 on any of the first

7 items, or a score ≥ 2 on two or more of any of the first 7 items) at any postbaseline visit will be summarized.

A listing will be provided for every abnormal movement scale. Listing for treatment emergent EPS will be provided.

3.9.5. Columbia-Suicide Severity Rating Scale (C-SSRS)

The C-SSRS is a questionnaire used to measure the presence and intensity of suicidal ideation and behavior. Suicidal behavior and suicidal ideation will be summarized descriptively (Table 10). The number of subjects with suicidal ideation and suicidal behavior will be summarized.

Supportive tabular display of subjects with all values will be provided.

Table 10: C-SSRS Categories for Analysis

Category	C-SSRS Item response is “YES”
Suicidal behavior ^a	Preparatory acts or behavior Aborted attempt Interrupted attempt Actual attempt Complete suicide
Suicidal ideation ^a	Wish to be dead Non-specific active suicidal thoughts Active suicidal ideation with any methods (not plan) without intent to act Active suicidal ideation with some intent to act, without specific plan Active suicidal ideation with specific plan and intent
Non-Suicidal Self-Injurious Behavior	Non-Suicidal Self-Injurious Behavior

^a Derived based on responses to individual items listed within the category

3.10. Pharmacokinetic/ Pharmacodynamic Data Analysis

Not applicable.

4. INTERIM ANALYSES

No interim analysis is planned for this study.

5. CHANGES IN CONDUCT OR PLANNED ANALYSES FROM THE PROTOCOL

To further assess the long-term durability, the following analysis was added in SAP but were not specified in protocol.

- Shift analysis in CGI-S

6. DEFINITIONS AND CONVENTIONS FOR HANDLING OF THE DATA

Dataset specifications will be provided in a separate document.

6.1. Analysis Visit Windows

Scheduled analysis visits are visits at scheduled timepoints as specified in the protocol ([Table 3 Schedule of Visits and Assessments](#)).

Scheduled analysis visits during the study period will be the same as the nominal visits collected in eCRF. There will be one valid value of assessment kept for each scheduled analysis visit in summary/analysis statistics.

Unscheduled visits are visits with data not collected on the scheduled time point. Unscheduled visits will not be used for by-visit summary/analysis statistics, unless specified otherwise.

All unscheduled visits as collected in eCRF will be included in listings.

Last postbaseline values are defined as the last valid postbaseline values collected for each subject during the treatment period.

An early termination (ET) visit during the on-treatment period can be mapped to a scheduled visit, if there is no valid value already at that visit. Visit windows are defined in [Table 11](#) and [Table 12](#). An ET visit that is not mapped will not be summarized in the tables or figures, but will be included in the listing.

Table 11: Visit Window for All Efficacy and Safety Assessments Excluding PANSS

Analysis Visit to be Mapped to	Target Study Week	Target Visit Day ^a	Visit Window
Visit 1	Week 0	Day 1	1
Visit 2	Week 2	Day 15	[2, 21]
Visit 3	Week 4	Day 29	[22, 35]
Visit 4	Week 6	Day 43	[36, 49]
Visit 5	Week 8	Day 57	[50, 70]
Visit 7	Week 12	Day 85	[71, 98]

Analysis Visit to be Mapped to	Target Study Week	Target Visit Day ^a	Visit Window
Visit 9	Week 16	Day 113	[99, 126]
Visit 11	Week 20	Day 141	[127, 154]
Visit 13	Week 24	Day 169	[155, 182]
Visit 15	Week 28	Day 197	[183, 210]
Visit 17	Week 32	Day 225	[211, 238]
Visit 19	Week 36	Day 253	[239, 266]
Visit 21	Week 40	Day 281	[267, 294]
Visit 23	Week 44	Day 309	[295, 322]
Visit 25	Week 48	Day 337	[323, 350]
Visit 27	Week 52	Day 365	[351, 371]

^a Visit Day is calculated as date of visit – date of the first dose of study drug + 1 day.

Table 12: Visit Window for PANSS Assessments

Analysis Visit to be Mapped to	Target Study Week	Target Visit Day	Visit Window
Visit 2	Week 2	Day 15	[2, 21]
Visit 3	Week 4	Day 29	[22, 42]
Visit 5	Week 8	Day 57	[43, 70]
Visit 7	Week 12	Day 85	[71, 126]
Visit 13	Week 24	Day 169	[127, 210]
Visit 19	Week 36	Day 253	[211, 308]
Visit 27	Week 52	Day 365	[309, 371]

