14.4. Safety and Tolerability Analyses

Incidence of AEs will be analyzed as a safety endpoint. Reported adverse event terms will be coded using the Medical Dictionary for Regulatory Activities (MedDRA) and summarized by system organ class and preferred term categories.

SAEs and AEs contributing to study discontinuation will also be summarized.

Observed values and change from baseline in weight, BMI, waist circumference, laboratory parameters, vital signs, and ECG parameters will be summarized by study visit.

The number and percentage of subjects who have met potentially clinically significant (PCS) criteria at any post-baseline visit will be summarized for laboratory, vital signs, weight, and ECG parameters. Supporting listings will be provided.

The number and percentage of subjects with shifts in laboratory and EPS parameters (AIMS, BARS, and SAS) will be summarized. Supporting listings will be provided.

The number and percentage of subjects with C-SSRS assessments of suicidal ideation and behavior will be summarized.

Prior and concomitant medication use will be summarized by World Health Organization (WHO) Drug Dictionary Anatomical Therapeutic Class (ATC) code.

Listings will be provided for all safety endpoints.

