3.9.2. Clinical Laboratory Parameters

Laboratory parameters will be presented in conventional (ie, US) units. Only scheduled laboratory parameters will be included in the summaries, unless specified otherwise. All laboratory data, including those collected at unscheduled visits, will be included in the listings.

Laboratory results including baseline and change from baseline during the treatment period for chemistry and hematology parameters will be summarized by visit.

Clinical laboratory test values, scheduled or unscheduled, will be considered potentially clinically significant (PCS) if they meet PCS criteria listed in [Table 3](#). The number and percentage of subjects who have postbaseline PCS clinical laboratory values will be summarized. The percentages will be calculated based on the number of subjects with non-PCS baseline value and have at least one postbaseline assessment. All PCS values including baseline PCS values will be included in supportive listings.

For selected metabolic parameters (fasting total cholesterol, fasting high density lipoprotein[HDL], fasting low density lipoprotein[LDL], fasting triglycerides, fasting glucose, and hemoglobin A1c[HbA1c]), an analysis of sustained PCS values will also be conducted. The percentage of subjects with sustained PCS values through the treatment period will be summarized. The denominator is all subjects with non-PCS at baseline and at least two postbaseline assessments, and the numerator is the number of subjects who met PCS criteria at the last 2 assessments within the treatment period.

Shift tables for selected fasting metabolic parameters (total cholesterol, LDL, HDL, triglycerides, glucose and HbA1c) and liver function tests will be presented. The criteria are summarized in [Table 4](#), [Table 5](#) and [Table 6](#).

Table 3: Criteria of Potentially Clinically Significant (PCS) Abnormality for Selected Analytes

Parameter	Criteria
Chemistry	
Albumin	<2.5 g/dL
Alkaline Phosphatase (U/L)	$\geq 3 \times \text{ULN}$
Alanine Aminotransferase (U/L)	$\geq 3 \times \text{ULN}$
Aspartate Aminotransferase (U/L)	$\geq 3 \times \text{ULN}$
Bilirubin, Total	$\geq 2.0 \text{ mg/dL}$
Blood Urea Nitrogen	>30 mg/dL
Cholesterol, Random	>300 mg/dL
Cholesterol, Fasting ^a	$\geq 240 \text{ mg/dL}$
Cholesterol, Fasting	Increase $\geq 40 \text{ mg/dL}$
Cholesterol, HDL Fasting	<40 mg/dL
Cholesterol, HDL Fasting	Decrease $\geq 20 \text{ mg/dL}$
Cholesterol, LDL Fasting	$\geq 160 \text{ mg/dL}$

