Cholesterol, LDL Fasting	Increase $\geq 30 \text{ mg/dL}$
Creatine Kinase (U/L)	$\geq 3 \times \text{ULN}$
Creatinine	$\geq 2.0 \text{ mg/dL}$
Glucose, Random	<50 mg/dL or $\geq 200 \text{ mg/dL}$
Glucose, Fasting	<50 mg/dL or $\geq 126 \text{ mg/dL}$
Glucose, Fasting	Increase $\geq 10 \text{ mg/dL}$
HbA1c	$\geq 5.7\%$
Potassium	<3 mmol/L or >5.5 mmol/L
Lactate Dehydrogenase (U/L)	$> 3 \times \text{ULN}$
Prolactin (Female)	>30 ng/mL
Prolactin (Male)	>20 ng/mL
Sodium	<130 mmol/L or >150 mmol/L

Table 3: Criteria of Potentially Clinically Significant (PCS) Abnormality for Selected Analytes (Continued)

Triglycerides, Fasting	≥200 mg/dL
Triglycerides, Fasting	Increase ≥50 mg/dL
Hematology	
Eosinophils	>1.0 × 10 ³ /μL
Hematocrit (Female)	≤32%
Hematocrit (Male)	≤37%
Neutrophils, Absolute	<1.5 × 10 ³ /μL
Platelets	<75.0 × 10 ³ cells/μL or ≥ 700.0 × 10 ³ cells/μL
Leukocytes	≤ 2.8 × 10 ³ /μL or ≥ 16.0 × 10 ³ /μL

^a reported fasting.

Table 4: Shifts Categories from Baseline to Any Postbaseline for Selected Lipid Parameters

Total Cholesterol (fasting) mg/dL
Normal (<200) to High (≥240)
Borderline (≥200 and < 240) to High (≥240)
Normal (<200) to Borderline (≥200 and <240)
LDL Cholesterol (fasting) mg/dL
Normal (<100) to High (≥160)
Borderline (≥100 and <160) to High (≥160)
Normal (<100) to Borderline (≥100 and <160)
HDL Cholesterol (fasting) mg/dL
Normal (≥40) to Low (<40)
Triglycerides (fasting) mg/dL
Normal (<150) to High (≥200)
Borderline (≥150 and <200) to High (≥200)
Normal (<150) to Borderline (≥150 and <200)

Table 5: Shift Categories from Baseline to Any Postbaseline in Glucose and HbA1c

Glucose (fasting) mg/dL
Normal (<100) to Impaired (≥ 100 and <126)
Normal (<100) to High (≥ 126)
Impaired (≥ 100 and <126) to High (≥ 126)
HbA1c %
Normal (<5.7%) to Borderline ($\geq 5.7\%$ and <6.5%)
Borderline ($\geq 5.7\%$ and <6.5%) to High ($\geq 6.5\%$)
Normal (<5.7%) to High ($\geq 6.5\%$)

Table 6: Shift Categories from Baseline to Any Postbaseline in Liver Function Test

Alanine Aminotransferase (ALT) (U/L)
Shift from Normal to ≥ 3 x ULN
Shift from Normal to ≥ 5 x ULN
Shift from Normal to ≥ 10 x ULN
Aspartate Aminotransferase (AST) (U/L)
Shift from Normal to ≥ 3 x ULN
Shift from Normal to ≥ 5 x ULN
Shift from Normal to ≥ 10 x ULN
Bilirubin, Total (mg/dL)
Shift from Normal to >1 x ULN
Shift from Normal to ≥ 2 x ULN

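### SAP 6.1 bars an unmapped early-termination visit from all tables and figures, not only by-visit ones, which conflicts with safety counts scoped to any postbaseline value

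*SAP*

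**What the plan says.** SAP 6.1 lets an ET visit in the on-treatment period take the place of a scheduled visit that has no valid value. For the rest it says: "An ET visit that is not mapped will not be summarized in the tables or figures, but will be included in the listing". The same section treats unscheduled visits more narrowly: "Unscheduled visits will not be used for by-visit summary/analysis statistics, unless specified otherwise". SAP 7 keeps unscheduled and repeated measurements out of by-visit tables and figures but admits them to the PCS analyses and the listings. It does not name ET visits.

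Several safety analyses have a wider scope than by-visit:

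- **PCS.** Protocol 14.4 covers labs, vital signs, weight and ECG with the words "met potentially clinically significant (PCS) criteria at any post-baseline visit will be summarized". SAP 3.9.2 applies the lab criteria to scheduled and unscheduled values alike.
- **Lab shifts.** Table 4 is titled "Shifts Categories from Baseline to Any Postbaseline for Selected Lipid Parameters", and Tables 5 and 6 have the same scope. SAP 3.9.2 also says: "Only scheduled laboratory parameters will be included in the summaries, unless specified otherwise".
- **Orthostatic, weight-PCS and EPS counts.** SAP 3.9.3.1, 3.9.3.2 and 3.9.4 count a finding at any visit after baseline.
- **Sustained PCS.** SAP 3.9.2: "The denominator is all subjects with non-PCS at baseline and at least two postbaseline assessments". The numerator is subjects who meet PCS at their last two assessments in the treatment period.

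Protocol 7.3 gives the ET visit the same assessments as Visit 27 and places it as near as possible to the last dose.

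**The concern.** The only stated objective is long-term safety and tolerability, and the ET visit is the end-of-treatment assessment of subjects who stop early. A programmer who follows the 6.1 sentence as written would drop that visit from every summary table whenever its window is already filled. The tables that should record whether a subject ever met a safety criterion would then miss a criterion first met at ET. No text in the SAP says which rule prevails for such a visit.

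**Working it through.** **Texts side by side, for an ET value in a filled window**

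| Analysis | Scope stated | 6.1 ET sentence read literally | ET treated as unscheduled or repeated |
|---|---|---|---|
| Lab PCS (3.9.2) | scheduled or unscheduled | out | in (3.9.2 and 7) |
| Vital-sign and ECG PCS (3.9.3.1, 3.9.3.3) | at least one postbaseline PCS value | out | in (7) |
| Weight PCS (3.9.3.2) | any postbaseline visit | out | in (7) |
| Orthostatic, EPS (3.9.3.1, 3.9.4) | any postbaseline visit | out | not barred by 6.1, though 7 does not name them |
| Lab shifts (Tables 4 to 6) | any postbaseline | out | open: turns on whether the table title overrides the scheduled-only rule in 3.9.2 |

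**Direction, ever-met counts.** A filled window means that the subject already has a valid postbaseline value, so dropping the ET value does not remove the subject from a denominator that needs one. The numerator can only fall or stay. Example: ALT is normal through Visit 13 (Day 169) and at least 3 x ULN at ET on Day 175, both in window [155, 182]. Literally, the ET value reaches neither the PCS table nor Table 6. Under SAP 7 it reaches the PCS table, and Table 6 remains open.

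**Direction, sustained PCS.** The HbA1c criterion is 5.7% or more.

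- Take 5.5% at Visit 7, 6.6% at Visit 13 (Day 169) and 6.6% at ET on Day 178. With the ET value the last two are 6.6% and 6.6%: sustained. Without it they are 5.5% and 6.6%: not sustained.
- If instead HbA1c is at or above 5.7% at Visits 7 and 13 and below it at ET, dropping the ET value turns a non-sustained subject into a sustained one.

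**Size, in days.** Inputs are the Table 11 windows, which are contiguous over Days 2 to 371. Assumptions: ET days are uniform over Days 2 to 364 (363 days), every scheduled visit is done on its target day, and labs, ECG and movement scales are done at Weeks 4, 12, 24, 36 and 52 (inferred from a schedule table that did not survive text extraction well). An ET day is unmapped if it falls after the target day and inside the same window.

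Days from target to window end are 6 for each of Visits 2, 3 and 4, and 13 for each of the 11 visits 5, 7, 9, ..., 25.

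- Weight and vital signs: 3 x 6 + 11 x 13 = 161; 161/363 = 44.4%.
- Labs, ECG and movement scales (Visits 3, 7, 13, 19): 6 + 3 x 13 = 45; 45/363 = 12.4%.

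Sensitivity to the visit window of plus or minus 2 days:

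- Visits 2 days early: 3 x 8 + 11 x 15 = 189 (52.1%) and 8 + 3 x 15 = 53 (14.6%).
- Visits 2 days late: 3 x 4 + 11 x 11 = 133 (36.6%) and 4 + 3 x 11 = 37 (10.2%).

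The longest gap from the valid value to the barred ET value is 13 days (15 early, 11 late).

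**Sustained-PCS denominator.** On ET Days 30 to 35 the barred lab would be only the second postbaseline assessment, so the subject leaves the denominator: 6/363 = 1.7% of days (4 to 8 days, 1.1% to 2.2%, with visits late or early).

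**The case against.** The strongest case on the other side is context. The sentence closes the mapping paragraph of a section on visit windows, and mapping only places a value in a visit row. SAP 7 speaks of by-visit tables and figures and admits unscheduled or repeated values to PCS. An ET value in a filled window is naturally one of these. The unscheduled-visit rule in 6.1 would then also leave it available to the orthostatic and EPS counts, so that reading helps beyond PCS. For lab shifts, leaving out an off-schedule value can be seen as the convention stated in 3.9.2. All of this stands as evidence of intent. It does not settle the matter, because the ET sentence is the more specific one, omits the limit that a neighbouring rule states, and is not mentioned in SAP 7.

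There is also mitigation. AE tables and listings are unaffected, clinically significant lab values are recorded as AEs (Protocol 13.1), EPS and suicidality have AE summaries (SAP 3.9.1.2), and the separate dataset and programming specifications may resolve the point.

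Three stronger inferences are not supported:

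- *That 44% of early terminators lose safety findings.* The figure is a share of calendar days under an assumed uniform spread. An ever-met result changes only if the criterion is first met between the valid value and the ET visit.
- *That discontinuing subjects at HbA1c of 6.5% or more (Protocol 7.3) hides HbA1c cases.* Where a scheduled lab triggers the withdrawal, that value is already in the PCS table and counts for Table 5. In that situation only sustained PCS can change.
- *That SAP 5 conceals a departure from the protocol.* It lists only the CGI-S shift, but if 6.1 was meant as a by-visit rule there is no departure to list.

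**Conclusion.** The point holds as a conflict of wording with a possible effect on results. Read literally, SAP 6.1 gives the wrong answer for analyses scoped to any postbaseline value. The probable intent is by-visit exclusion, but the text does not say so. The orthostatic and EPS counts conflict with the literal sentence and are not named in SAP 7; the lab shifts are the least certain case.

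Ever-met counts can only be lowered or left unchanged; sustained PCS has no fixed direction. The number of subjects affected cannot be derived, since the documents give neither the dropout rate nor its timing. The shares of 44% (37% to 52%) and 12% (10% to 15%) of possible ET days rest on the uniform-timing and visit-date assumptions above, and the short gap to a valid value limits the effect.

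**What to change.** Replace the last sentence of the ET paragraph in SAP 6.1 with wording such as:

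*A value from an early-termination visit that has not been mapped is left out of by-visit summary tables and figures only. It counts in the PCS and sustained-PCS analyses, in the any-postbaseline lab shift (Tables 4 to 6), orthostatic, weight-PCS and EPS summaries, and in last-postbaseline values, and it is listed.*

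Leave the mapping rule and the visit windows as they are. Where an analysis already carries a treatment-period limit (sustained PCS, last-postbaseline values), that limit stays.

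Do not bring in the 7-day TEAE limit from SAP 3.9.1 as part of this change. SAP 6.1 maps only on-treatment ET visits, so a new cut-off could alter which visits are mapped and hence the by-visit tables. Nor should later ET values be made listing-only: Protocol 14.4 and SAP 3.9.2 set no limit in days on PCS counts, so that could lower them again.

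The cost is one sentence, with no new data or visits. By-visit tables do not change. Some ever-met counts may come out slightly higher, and sustained PCS may move in either direction.

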3.8.3. Other Endpoints

- Change from baseline in IWQOL-Lite scales (total score, physical function, self-esteem, sexual life, public distress, and work) by visit
- Change from baseline in EQ-5D-5L index value and visual analogue scale (VAS) score by visit

Descriptive statistics of IWQOL-Lite scales and EQ-5D-5L, including n, mean, SD, median, minimum, and maximum, will be summarized by visit based on observed data.

The IWQOL-Lite scale is a 31-item self-report measure of obesity-specific quality of life. IWQOL-Lite provides an overall total score as well as scores on five domains: (1) physical function, (2) self-esteem, (3) sexual life, (4) public distress, and (5) work. The raw scores will be transformed as follows (Tessier et al, 2012)³: the transformed scores range from 0 to 100, with 100 representing the best, and 0 representing the most impaired quality of life.

$$Transformed\ Score = \frac{maximum\ theoretical\ score - actual\ score}{test\ score\ range} \times 100$$

The EQ-5D-5L is a validated quality of life questionnaire developed by the EuroQol Group in order to provide a simple, generic utility measure for characterizing current health states of patients. EQ-5D-5L is designed for self-completion by subjects. It consists of 2 parts – the EQ-5D-5L descriptive system and the VAS.

The EQ-5D-5L descriptive system comprises 5 dimensions: mobility, self-care, usual activities, pain/discomfort, and anxiety/depression. Each dimension has 5 levels.

The 5 dimensional 5-level systems are converted into an index value. Values for theoretically possible health states are calculated using a regression model and weighted according to the social preferences of the U.S. population (Van Hout et al, 2012)⁴. The VAS records the respondent's self-rated health on a vertical VAS. The VAS has 100 (Best health you can imagine) at the top, and 0 (Worst health you can imagine) at the bottom. This information can be used as a quantitative measure of health outcomes as judged by the individual respondents. EQ-5D-5L self-reported VAS data generates information on the self-perceived overall health-related quality of life. Change from baseline in EQ-5D-5L index value and VAS score will be analyzed.

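### SAP Table 11 does not fit the measures taken at only five visits, and the Section 6.1 exclusion of unmapped early-termination values is not limited to by-visit tables

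*SAP*

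**What the plan says.** Table 11 in SAP Section 6.1 is titled "Visit Window for All Efficacy and Safety Assessments Excluding PANSS". It has 15 postbaseline windows, for Visits 2 to 5 and every odd visit from 7 to 27. PANSS alone has a separate set, Table 12.

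For early termination, Section 6.1 says that an ET "visit during the on-treatment period can be mapped to a scheduled visit, if there is no valid value already at that visit". Of the remainder it says: "An ET visit that is not mapped will not be summarized in the tables or figures, but will be included in the listing". The same section explains that "Scheduled analysis visits are visits at scheduled timepoints as specified in the protocol", and adds a definition that is not tied there to any table: "Last postbaseline values are defined as the last valid postbaseline values collected for each subject during the treatment period".

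Other sections bear on where an ET value can appear:
- SAP 3.9.2: "Only scheduled laboratory parameters will be included in the summaries, unless specified otherwise". For PCS, however, it counts unscheduled laboratory values too, and Section 7 repeats this for PCS analyses.
- SAP Tables 4 to 6 and Section 3.9.4: laboratory shifts and treatment-emergent extrapyramidal symptoms (EPS) are judged at any postbaseline point.
- SAP 3.8.3: for IWQOL-Lite and EQ-5D, the descriptive statistics listed through "minimum, and maximum, will be summarized by visit based on observed data" are the only tables.
- SAP 3.9.3.3: ECG has an end-of-treatment summary. The laboratory and movement-scale sections give no such row for change scores.
- Protocol 7.3: the ET visit repeats the Visit 27 assessments, on whatever day it falls.

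**The concern.** Table 11 matches the treatment-period schedule for weight, waist and vital signs in Protocol Table 3. Ten of its 15 postbaseline windows belong to visits where laboratory tests, ECG, AIMS/BARS/SAS, IWQOL-Lite and EQ-5D are not taken. Unscheduled values are kept out of by-visit summaries, so any laboratory or rating-scale row at those ten visits can hold only mapped ET values. A Week 28 laboratory mean, for example, would describe only subjects who stopped around then. It would sit between Week 24 and Week 36 rows made up largely of continuing subjects, and be split again by treatment sequence.

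The second problem is what happens when the window's slot is already filled. The ET value is then barred from tables and figures generally, although the shift and treatment-emergent EPS analyses are meant to use any postbaseline value. The primary objective is long-term safety and tolerability, and ET values come from the subjects who did not stay on treatment.

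**Working it through.** **Inputs.** Windows and target days are from SAP Tables 11 and 12. The five-visit schedule (Visits 3, 7, 13, 19, 27) is from Protocol Table 3. The movement-scale, IWQOL and EQ-5D rows show Visit 13 directly. In the text extracted from the PDF, the laboratory and ECG rows have that mark one column early, as does the urine drug screen row; footnote e names Visit 13 for the drug screen, so I read all of them as Visit 13.

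**Assumptions.** ET can fall on Days 2 to 364, which is 363 days, and scheduled visits occur on their target day. The SAP states neither, and it gives no figure of its own to reproduce.

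**Table 11, five-visit measures.**

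| ET day falls in | Count | Days | Share of 363 |
|---|---|---|---|
| Window of a visit where the measure is not scheduled | V2 20 + V4 14 + V5 21 + 7 × 28 (V9, V11, V15, V17, V21, V23, V25) | 251 | 69.1% |
| Scheduled window, before target day (joins that row) | 7 + 14 + 14 + 14 + 14 | 63 | 17.4% |
| Scheduled window, on or after target day (slot filled) | 7 + 14 + 14 + 14 | 49 | 13.5% |

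Check: 251 + 63 + 49 = 363.

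**Same count for measures that fit their table.** Weight, waist and vital signs have 0 off-schedule days on Table 11. PANSS has 0 on Table 12 (188 joining, 175 filled). On Table 11, PANSS would have had 210 of 363 (57.9%).

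**Two readings of Section 6.1.**
- Plain reading (an ET visit maps to any Table 11 visit with no value yet): 251 days give rows of early terminators only and 49 days are unmapped.
- Stricter reading (the measure itself must be scheduled at that visit): 251 + 49 = 300 days unmapped, 300/363 = 82.6%.

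**Row size on the plain reading.** Per 100 ET visits spread evenly over the 363 days, each 28-day off-schedule row holds 100 × 28/363 = 7.7 subjects. The Visit 2, 4 and 5 rows hold 5.5, 3.9 and 5.8.

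**Before Visit 3 (Days 2 to 28).** The ET value is normally the only scheduled postbaseline value of these measures. On 20 of the 27 days it falls in the Visit 2 window.

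**Sustained PCS.** The denominator needs two postbaseline assessments. On Days 29 to 84 the subject has one scheduled value, so the ET value decides entry. Those 56 days split into 7 filled, 35 off-schedule and 14 joining. On the plain reading the ET value is unmapped on 7 of them.

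**Sensitivity of the 69.1%.**
- Other ET-day ranges: 67.8% (Days 2 to 371) to 71.9% (Days 2 to 350).
- All visits 2 days early: 251/361 = 69.5%. All 2 days late: 251/365 = 68.8%.
- Days weighted by an assumed Weibull stopping time (shape 0.6 to 1.2, 25 to 45% stopping): 68.7 to 70.8%.

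**Windows by Table 12's midpoint rule.** In Table 12 the midpoint day between two target days opens the later window. For targets 29, 85, 169, 253 and 365 the midpoints are 57, 127, 211 and 309. This gives Visit 3 [2,56], Visit 7 [57,126], Visit 13 [127,210], Visit 19 [211,308] and Visit 27 [309,371]; the last three equal Table 12. Result: off-schedule 0; joining 27 + 28 + 42 + 42 + 56 = 195 (53.7%); filled 28 + 42 + 42 + 56 = 168 (46.3%).

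**The case against.** **Most ET values do reach a table.** A reader might infer that 82.6% of ET days are lost from the tables. The text does not support that. Section 6.1 maps a visit to a visit, Visit 15 is a scheduled visit, and Table 11 says it covers these assessments. The stricter reading adds a condition that Section 6.1 does not state. On the plain reading only the 49 filled-slot days are unmapped. This stands.

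**The safety signal is largely caught elsewhere.** Most high-category shifts use PCS cut-offs: total cholesterol 240, LDL 160, HDL 40, triglycerides 200, fasting glucose 126, HbA1c 5.7%, ALT and AST 3 × ULN. PCS counts unscheduled values, so an ET laboratory value that newly crosses one of these is tabulated anyway. ECG has PCS and an end-of-treatment summary, EPS is also analysed as adverse events, and every value is listed. This stands too. It does not cover borderline shifts, HbA1c of 6.5% or more, the higher ALT/AST tiers, bilirubin shifts, or EPS defined on the rating scales.

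**The specific wording favours inclusion.** A sensible programmer would let the any-postbaseline wording win, and Protocol Table 3 has an ET column, so ET tests are arguably scheduled. Both are fair, but the 6.1 sentence has no exception. Only PCS has an explicit one.

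**Other documents may settle it.** Dataset and programming specifications and mock tables are deferred to separate documents. They may fix the rows, but the SAP states the windows and the exclusion itself and should make them agree.

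**Wider windows are a trade-off.** They raise filled-slot days from 49 to 168 and move some values further from the nominal week. This is correct, so the windows should not be adopted alone.

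**Conclusion.** The concern holds in limited form. Table 11 gives the five-visit measures a grid built for a denser schedule, while PANSS, also sparse, has its own. On the plain reading, 69% of possible ET days lead to rows made up only of early terminators. On a further 13.5% the ET value is barred from tables by a sentence that conflicts with the any-postbaseline analyses.

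The exposed results are mainly treatment-emergent EPS on the rating scales; the borderline, HbA1c 6.5%, higher ALT/AST and bilirubin shifts; sustained PCS; by-visit change scores; and IWQOL-Lite and EQ-5D. Ordinary PCS rates, and most high-category shifts that share their cut-offs, are not in doubt.

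The percentages are shares of calendar days under the stated assumptions. The documents give no stopping times, so they do not forecast shares of subjects or of lost data. The study is descriptive and no test is affected. The change should be made because the affected rows and counts describe subjects who stopped early in a safety study.

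**What to change.** 1. Limit the Section 6.1 sentence on unmapped ET visits to by-visit displays. State that all on-treatment ET values, mapped or not, count in the PCS, sustained-PCS, any-postbaseline shift and treatment-emergent EPS analyses. This alone removes the conflict for those analyses.
2. Add a window table for laboratory tests, ECG, AIMS/BARS/SAS, IWQOL-Lite and EQ-5D with the five midpoint windows derived above. With it, add the last-postbaseline row, using the existing 6.1 definition, to the by-visit tables of these measures.

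The cost is one table, a few sentences and the mapping code, with no new data. Some ET values will sit further from the nominal week: a Day 3 laboratory value would show as Week 4, much as Table 12 already shows a Day 309 PANSS as Week 52. Filled-slot days become 168 of 363 (46.3%), close to the 175 of 363 (48.2%) that Table 12 gives for PANSS. The last-postbaseline row covers them, which is why the two parts of item 2 belong together. All 27 days before Visit 3 then map to Visit 3.

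The SAP also leaves the on-treatment period for ET mapping undefined. That is a minor wording point, and this fix does not depend on it.
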